2.2 Overview of Proposed Study

This is a pilot RCT (1:1 randomization) of a remote perioperative telemonitoring intervention in major abdominal cancer surgery. We will focus on GI malignancies, because the surgical procedures, extent of resection, and expected surgical outcomes are similar. In Aim 1, we will assess the feasibility, retention, and acceptability of the intervention through statistics of participation, intervention completion (retention) rates, and qualitative data from exit interviews. In Aim 2, surgical outcomes (post-operative complications), healthcare utilization (postoperative complications, hospital readmissions), PROs (symptoms, QOL), and functional recovery (pedometer steps) will be examined by treatment arm. Our primary endpoint is severity (grade) of postoperative complications from discharge to day 30 post-discharge. This study will be conducted in compliance with the protocol, Good Clinical Practice (GCP) and the applicable regulatory requirements.

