11.0 Endpoint Evaluation Criteria/Measurement of Effect

11.1 Response Criteria

Outcome Measures – Outcomes are assessed before surgery (baseline), before discharge, and until 30 days post-discharge (**Table 1**). Measures were selected based on reliability/validity, our preliminary studies, and brevity to minimize burden. ePROs will take about 4-7 minutes to complete. We will also obtain sociodemographic, clinical (diagnosis, tumor stage, neoadjuvant treatments, Charlson-Deyo co-morbidity index, time to adjuvant treatment), and surgical (Pre-op ECOG performance score, procedure, open or minimally invasive, ASA classification, date of surgery, post-op admission status and date, ICU days, post-operative events, discharge date, discharge status) data for all patients.

Table 1. Outcome Measures by Aims and Assessment Time Points

	Measures	Before Surgery (T1)	Pre-Discharge (T2)	Day 2 (T3)	Day 7 (T4)	Day 14 (T5)	Day 30 (T6)
SA 1 (Feasibility, Retention and Acceptability)	Participation Rate - % of eligible consented, reasons for non-participation, dropout and lost to follow-up rates, reasons for dropout, differential dropout by treatment arm.						Throughout study period
	Telemonitoring Completion Rate – number of PGHD and ePRO assessments completed ($\geq 70\%$)						Throughout study period
	Patient Experience – Semi-Structured Exit Interview Guide						X
SA 2 (Preliminary Efficacy)	Post-Operative Complications – Comprehensive Complications Index (CCI) ^{131, 132}		X	X	X	X	X
	Hospital Readmissions				X	X	X
	General Symptoms - MD Anderson Symptom Inventory (MDASI) ^{55, 120}	X	X	X	X	X	X
	Disease-Specific Symptoms – MDASI Symptom Library	X	X	X	X	X	X
	QOL – EQ-5D-5L ^{10,113,121-125}	X	X	X	X	X	X
	Functional Activity (daily steps taken) ¹²⁷⁻¹³⁰						Throughout study period

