12.1.3 Data Collection Forms and Submission Schedule

All data will be collected from home monitoring devices, wearable devices (pedometer), and electronic PROs. Data will be sent to the location identified in Section 12.1.1 and stored in a secure location.

EQ-5D-5L - This validated tool evaluates five QOL variables: mobility, self-care, usual activities, pain/discomfort, and anxiety/depression. One final item evaluates overall health state using a visual analogue scale with the end points labeled best to worst imaginable health state (0-100 numeric value). The EQ-5D has been widely used in clinical trials and also used in quality-adjusted survival analysis.²⁴⁻²⁷

MD Anderson Symptom Inventory (MDASI) - This is a brief, validated measure of 13 common cancer-related symptoms with severity of each rated on a 10-point scale. Patients also rate how much their symptoms interfered with 6 common functional domains. The MDASI has several advantages over other symptom-assessment scales in that it applies broadly across cancer types and treatments, is easy for patients to complete, and includes items related to symptom interference with daily life. Cronbach alpha reliability ranges from 0.82 to 0.94.^{28,29}

Sociodemographic and health status – This tool covers social and demographic factors, including patient's age, sex, race/ethnicity, education, marital status, living situation, employment, income, religious preference, tobacco history, and symptoms. Patients will complete the tool at baseline.

Satisfaction Tool – This patient self-reported measure contains 13 questions designed to assess satisfaction with the electronic assessment. Data captured include: 1) ease of use of web-based surveys and wristband device; 2) Feedback on items in the web-based surveys that are distressing or difficult to comprehend; 3) Feedback on length of surveys and timing of administration; and 4) Suggestions for items that were not covered but should be added. It will be administered at the Day 30 post-discharge assessment. Both arms of the study will undergo this.

Surgical Outcomes: Comprehensive Complications Index (CCI) - The CCI® summarizes the entire patient postoperative experience with respect to complications (on a scale from 0 to 100), and is based on the established Clavien-Dindo classification. The CCI® was validated in a study with 1299 participants, and external validity was tested in a randomized trial evaluating pancreas, esophageal, and colon resections.^{31,32}

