13.0 Statistical Considerations

13.1 Study Design

13.1.1 Sample Size Calculation and Power Analysis

We will need 128 patients (64 per arm) to detect an effect size of 0.5 in the primary outcomes as described in Aim 2 (postoperative complications, lower readmission rates, improved symptoms, QOL, and functional recovery) between the two groups, with a two-sided 0.05 significance level using a two-sample t-test and at least 80% power. We will enroll a total of 160 (80 per arm to account for an expectation of 20% attrition. Thus, we will have sufficient power for all primary outcomes, including our primary endpoint of postoperative complications.

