Feasibility will be assessed through: 1) the ratio of eligible participants to those enrolled and those who declines participation; 2) reasons for non-participation; 3) number of scheduled study encounters completed; 3) attrition rate between pre- and post-discharge; 4) reasons for attrition/dropout; 5) the ratio of all participants to those who completed $\geq 70\%$ of the study; These data will be descriptively reported and analyzed. Qualitative data on acceptability from exit interviews will be analyzed using the conventional content analysis approach.⁶⁵ This approach is used to describe a phenomenon where existing theory or research literature is limited. Data from the audio-recorded interviews will be transcribed and analyzed using HyperRESEARCH™ qualitative software. Transcripts will be imported allowing for the development of analytic categories, data coding, and review of coded data. All data will be read repeatedly to achieve immersion and obtain a sense of the whole. Then, data will be read word by word to derive codes. Codes will then be sorted into themes based on links and relationship. Separate investigators ([name] and [name]) will conduct a final validation review of the codes and themes to ensure consistency and clarity across all qualitative data. Data discordantly coded will be discussed for refinement and consensus purposes.

Specific Aim 2: Determine the preliminary efficacy of the remote perioperative telemonitoring intervention on surgical outcomes, healthcare utilization, PROs, and functional recovery.

Hypothesis 2.1: Patients randomized to the telemonitoring arm will experience reduced severity (grade) of postoperative complications, lower readmission rates, and improved symptoms, QOL, and daily steps.

For Specific Aim 2, the primary endpoint is the change in Comprehensive Complications index (CCI) from discharge to day 30 post-discharge. First, change in CCI will be computed. A two-sample t-test will be conducted to determine if there is significant difference between mean CCI of the intervention arm and the control arm. Trends in CCI scores will be explored over time (T2-T5). Exploratory within subjects' correlation will be examined using Pearson correlation between adjacent time points. A random-effects model will be used to study group differences in mean over time. Other variables (e.g., age and sex) may be included in the model to adjust for possible confounding.

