Similar analysis will be carried out for repeatedly measured secondary endpoints (symptom severity score, QOL). Generally speaking, we expect better scores in the intervention arm than the control arm. Healthcare resource use (e.g., hospital readmission) is a secondary endpoint. At each time point, we will estimate the ER visits/readmission rates and provide confidence intervals for each arm. Further, a binomial test for comparing two proportions will be conducted to see if there is significant difference between the readmission rates of the two arms. For simplicity, Bonferroni correction will be used both in the proportions comparisons test and the confidence intervals construction.

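### Symptoms and QOL inherit two between-arm analyses with no deciding score or contrast, and the inherited change-from-discharge t-test can subtract away a treatment effect already present at discharge

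*Combined protocol and SAP*

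**What the plan says.** For Specific Aim 2, section 13.2.1.2 defines the primary endpoint as change in CCI from discharge to day 30. It computes that change, compares arms by a two-sample t-test, says trends and adjacent-visit correlations will be explored, and adds: "A random-effects model will be used to study group differences in mean over time". Covariates such as age and sex are optional. Symptoms and QOL are then covered by one sentence: "Similar analysis will be carried out for repeatedly measured secondary endpoints (symptom severity score, QOL". Bonferroni appears only in the text that follows, on readmission and ER proportions and their intervals.

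More than one score is available in each domain. Table 1 in section 11.1 lists general MDASI and, on its own row, "Disease-Specific Symptoms – MDASI Symptom Library". Section 12.1.3 describes 13 MDASI severity items, 6 interference domains and five EQ-5D-5L dimensions, and then: "One final item evaluates overall health state using a visual analogue scale".

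The status of these outcomes is inconsistent. Section 13.1.1 says "We will need 128 patients (64 per arm) to detect an effect size of 0.5 in the primary outcomes as described in Aim 2" and includes symptoms and QOL in that list, at a "two-sided 0.05 significance level using a two-sample t-test and at least 80% power". The opening of 13.2.1.2 also counts them among the primary outcomes for hypothesis testing. The sentence that gives their analysis calls them secondary.

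On timing, section 1.0 has telemonitoring begin before surgery and continue through the hospital stay. Section 5.1 randomizes patients after the pre-surgery baseline assessment (T1) and repeats the PROs before discharge (T2).

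**The concern.** Two things are left open. First, a claim that symptoms or QOL improved could rest on the t-test or on some term of the model, for whichever score is taken to represent the domain. Nothing in the plan limits the error rate of that choice.

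Second, the two analyses ask different questions. If the CCI template is carried over as it stands, the t-test compares change since discharge. For symptoms and QOL, discharge is not a baseline: by then patients have been randomized and the intervention has started. Any benefit already present at discharge is subtracted out. A difference averaged over visits keeps that benefit but dilutes one that builds up late. The same data can therefore give opposite answers.

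Section 1.0 says the results will be used to refine the Phase III design, including the effect size for its sample size. A contrast picked after seeing the data would bias that effect size upward. A contrast that removes part of the effect would bias it downward.

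**Working it through.** **1. The plan's own figure.** The inputs are d = 0.5, two-sided alpha 0.05, 80% power and 1:1 allocation (sections 13.1.1 and 2.2). The noncentral-t calculation gives 63.77, so 64 per arm and 128 in total, with power 80.1%. Inflation for attrition is 128 / (1 - 0.20) = 160. Both figures reproduce. They assume one test at 0.05.

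**2. False-positive risk.** For k independent tests at 0.05 the risk is 1 - 0.95^k: 9.75% for k = 2 and 18.5% for k = 4. The documents give no correlations, so correlated normal test statistics were simulated (1,000,000 draws) over assumed values: 0 to 0.9 between the two tests on one score, and 0 to 0.7 between scores.

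| Reading | Any p < 0.05 under no effect |
|---|---|
| One score, both tests | 7.0% to 9.8% |
| One score per domain, one test each | 8.3% to 9.8% |
| One score per domain, both tests | 11.6% to 18.5% |
| Four scores, both tests | 17.8% to 33.7% |

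How much the second test adds depends on the undefined model contrast. With five visits and an assumed visit correlation of 0.3 to 0.7, the change t-test correlates 0 with an all-visit average, about 0.1 to 0.3 with a post-discharge average, and about 0.8 to 0.97 with a discharge-corrected average or a slope.

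**3. Power of the two analyses.** Assume 64 per arm, unit SD at each visit and an equal within-patient correlation r = 0.5. Table 1 has five visits from discharge onward (discharge, days 2, 7, 14 and 30). The list in 13.2.1.2 omits day 2 and so has four.

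- SD of change = sqrt(2(1 - r)) = 1.0.
- SD of the all-visit average = sqrt((1 + 4r)/5) = 0.775 for five visits, and sqrt((1 + 3r)/4) = 0.791 for four.
- Effect of 0.5 SD at discharge and maintained: mean change is 0.5 - 0.5 = 0, so the t-test rejects at its 5% level whatever r is. The average gives 0.5/0.775 = 0.645.
- Effect growing from 0 to 0.5 SD linearly in days: change gives 0.5/1.0 = 0.5. The five-visit mean effect is 0.5 x (0 + 2 + 7 + 14 + 30)/30/5 = 0.177, and 0.177/0.775 = 0.228. With four visits it is 0.2125/0.791 = 0.269.
- Effect growing in equal steps by visit: mean effect 0.25, giving 0.323 (five visits) or 0.316 (four).

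| Effect pattern | Change t-test | All-visit average, 5 visits | All-visit average, 4 visits | Day-30 difference |
|---|---|---|---|---|
| Maintained from discharge | 5% | 95% | 94% | 80% |
| Growing, linear in days | 80% | 25% | 33% | 80% |
| Growing, equal steps by visit | 80% | 44% | 43% | 80% |

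The last column uses d = 0.5 at day 30 with no credit for adjustment. Adjusting for T1 can only help in expectation: if T1 and day 30 correlate 0.5, d becomes 0.5/sqrt(1 - 0.25) = 0.577 and power about 90%.

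**4. After the fix.** One contrast per domain at 0.05 still leaves 8.3% to 9.8% across the two domains. At 0.025 each, the risk is 1 - 0.975^2 = 4.94% if independent, and at most 5% in any case. Unadjusted t-test power at d = 0.5 and alpha 0.025 is 71.2% with 64 per arm and 81.5% with 80 per arm. Reaching 80% needs 78 evaluable per arm.

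**The case against.** A hierarchy can be read into 13.2.1.2. The t-test comes first and is tied to the endpoint, while the model follows sentences about exploring trends and so may be only supportive. That reading is fair. It removes the second test, but it makes the change-from-discharge t-test the deciding analysis, which is the weaker choice if any benefit exists by discharge.

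The plan also does not say that change for symptoms and QOL starts at discharge. Unlike CCI, they have a T1 value, and a similar analysis could start there. That stands too, so the 5% power figure is conditional on the CCI template being carried over. A full effect at discharge is also an extreme case; how much benefit would be present by then is unknown.

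A reader might infer a false-positive risk near 30%. The documents do not support that as a property of the plan. It needs about four separately tested scores, whereas 13.2.1.2 refers to a symptom severity score in the singular and the instrument lists do not say that each score is tested. Nor is the 0.05 level stated for these endpoints in the analysis text. It is inferred from 13.1.1, the only place in the statistical section that gives a level.

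Finally, Aim 2 is labelled preliminary efficacy in a pilot, and no go/no-go rule hangs on a PRO p-value. This lowers the stakes. It does not remove the gap, because 13.1.1 claims sufficient power for these same outcomes as primary.

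**Conclusion.** The point holds as an unspecified deciding analysis combined with a poorly suited inherited test. No score, contrast or multiplicity rule is fixed for symptoms or QOL, and their primary or secondary status is contradictory. If both tests are read at 0.05, the false-positive risk is about 7-10% for one score and about 12-19% for one score per domain, over the assumed correlations.

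The choice of contrast matters more than these percentages. At 64 per arm and an assumed within-patient correlation of 0.5, power for a maintained effect is 5% by the change t-test and about 95% by an all-visit average. For an effect growing to 0.5 SD by day 30 it is 80% against roughly 25-44%, depending on growth shape and number of visits. A day-30 difference keeps about 80% under every one of these patterns. This should be corrected before analysis, but it does not invalidate the trial.

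**What to change.** In section 13.2.1.2, replace the sentence on symptoms and QOL with a self-contained specification:

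- One repeated-measures model per domain, adjusted for the T1 value already collected, in place of the separate t-test.
- One pre-named score and one pre-named contrast per domain. The day-30 between-arm difference is one suitable contrast. For scores, the mean of the 13 MDASI severity items and the EQ-5D-5L VAS are possible choices.
- Either Holm or Bonferroni across the two domains, or a statement that about 8-10% error across both remains and that no confirmatory claim will be made.
- All other scores, visits and model terms labelled exploratory and reported as estimates with 95% intervals.

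Reconcile the primary and secondary labels between 13.1.1 and the two places in 13.2.1.2, and align the visit list there with Table 1.

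The cost is SAP wording only, with no new data, visits or patients. Fewer results can be called significant, and an effect confined to early visits is described and not tested. If alpha is split, power at d = 0.5 falls to about 71% with 64 per arm before any gain from T1 adjustment, so the sufficient-power statement in 13.1.1 would need to be qualified.

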10.0 Study Calendar

	Baseline (T1)	Before Surgery	Treatment	Before Discharge (T2)	Day 2 Post- Discharge (T3)	Day 7 Post- Discharge (T4)	Day 14 Post- Discharge (T5)	Day 30 Post- Discharge (T6)
Informed Consent	X							
Baseline Assessment	R							
DAY OF SURGERY			X					
Post-Operative Complications – Comprehensive Complications Index (CCI) ^{131, 132}				R	R	R	R	R
Hospital Readmissions					R	R	R	R
General Symptoms - MD Anderson Symptom Inventory (MDASI) ^{55, 120}	R			R	R	R	R	R
Disease-Specific Symptoms – MDASI Symptom Library	R			R	R	R	R	R
QOL – EQ-5D-5L ^{10,113,121-125}	R			R	R	R	R	R
Semi-Structured Exit Interview/Satisfaction Tool								R
Functional Activity (daily steps taken) ¹²⁷⁻¹³⁰	Throughout study period							

X= Standard of care, R =Research

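### The readmission analysis applies Bonferroni without naming the family, divisor or deciding time point; one discharge-to-day-30 test at 0.05 would answer the stated question with more power

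*Combined protocol and SAP*

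**What the plan says.** Under Specific Aim 2, section 13.2.1.2 calls healthcare resource use a secondary endpoint and sets out three steps.

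- Estimation: "At each time point, we will estimate the ER visits/readmission rates and provide confidence intervals for each arm".
- Comparison: "a binomial test for comparing two proportions will be conducted to see if there is significant difference between the readmission rates of the two arms". No time point is attached to this test.
- Multiplicity: "Bonferroni correction will be used both in the proportions comparisons test and the confidence intervals construction". No family or divisor is given.

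The places that could supply the divisor differ:

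| Place | Post-discharge time points for readmission |
|---|---|
| Study Calendar (section 10.0), row "Hospital Readmissions" | days 2, 7, 14, 30 (four) |
| Table 1 (section 11.1), same row | days 7, 14, 30 (three; day 2 blank) |
| Time-point list opening section 13.2.1.2 | days 7, 14, 30 (three; day 2 not listed) |
| Chart audit (section 12.1.3) | 30-, 60- and 90-day readmissions, plus ER visits |

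ER visits have no row in either schedule. The status of readmission also varies: section 13.1.1, the matching synopsis text and the opening of section 13.2.1.2 count it among the primary outcomes, while the Aim 2 text calls it secondary.

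**The concern.** Hypothesis 2.1 asks one thing about readmission: is the rate lower with telemonitoring? The analysis text does not turn this into one decision. Correcting a test for multiplicity implies more than one test, and the only repetition that the paragraph mentions is over time points. The reader must infer how many tests there are, which one decides, and whether the rates are cumulative or per interval. On the per-interval reading, no test addresses readmission over the whole 30 days.

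Two things are at stake. First, the decision rule for day-30 readmission cannot be reproduced from the plan, because the divisor would have to be chosen later and could decide the result. Second, any correction over visits takes power from the single question asked and widens the per-arm intervals. Section 1.0 says the pilot is meant to inform the effect size and design of a Phase III trial, and for that purpose the per-arm rates serve as estimates.

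**Working it through.** **The plan's own figure.** Section 13.1.1: "We will need 128 patients (64 per arm) to detect an effect size of 0.5", "with a two-sided 0.05 significance level using a two-sample t-test and at least 80% power". The normal approximation gives n = 2 × ((1.960 + 0.842)/0.5)² = 62.8, so 63 per arm. The exact t-test needs 63.77, so 64, with power 0.801. Attrition: 128/(1 − 0.20) = 160, or 80 per arm. The figure reproduces, at an unadjusted alpha of 0.05. No alpha, divisor or power is stated for readmission, so there is nothing further to reproduce.

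**Alpha for the day-30 test, if the family is the visits.**
- Three visits: 0.05/3 = 0.0167, z = 2.394.
- Four visits: 0.05/4 = 0.0125, z = 2.498.

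**Can the divisor change the verdict?** Take 15/64 versus 5/64.
- Pooled rate 20/128 = 0.15625.
- Standard error √(0.15625 × 0.84375 × 2/64) = 0.0642.
- z = (10/64)/0.0642 = 2.434, two-sided p = 0.0149.

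This is significant with divisor 3 and not with divisor 4.

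**Power of the day-30 test, 64 per arm.** The documents give no planning rate for readmission, so the rates are assumptions. Power = Φ((d − z × se0)/se1), with se0 the pooled and se1 the unpooled standard error of the difference. The first scenario is about 33% versus 12.7%, an arcsine effect size of 0.5. At 33.3% and 12.77%, d = 0.2056, se0 = 0.0745 and se1 = 0.0722.

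| Assumed rates | alpha 0.05 | 0.05/3 | 0.05/4 |
|---|---|---|---|
| 33% vs 12.7% | 80% | 65% | 61% |
| 33% vs 17% | 59% | 41% | 37% |
| 20% vs 10% | 35% | 21% | 18% |

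The middle row is computed at one third versus one sixth. Summing exact binomial probabilities moves these values by no more than about two points; the last entry becomes 17%.

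**False-positive rate when every visit is tested on cumulative counts.** These come from simulation with 64 per arm, no true difference, rates of 33% or 20%, and an assumed 12%, 40%, 65% and 100% of readmissions occurring by days 2, 7, 14 and 30.
- With Bonferroni: 2.8% to 3.9%.
- Without correction: about 11% (three visits) or 13% to 14% (four visits).

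**Width of the per-arm intervals.** Half-width = z × √(p(1 − p)/n), so the ratio to a 95% interval does not depend on p or n.
- Divisor 3: 2.394/1.960 = 1.22.
- Divisor 4: 2.498/1.960 = 1.27.
- Example, p = 20% and n = 64: 9.8 points at 95%, 12.0 with divisor 3, 12.5 with divisor 4.

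**The case against.** The strongest reply is that the plan never says the readmission test is repeated by visit. The time-point phrase governs the estimation sentence, and the test is written in the singular. The family might instead be ER visits plus readmissions, or the 30-, 60- and 90-day windows. That stands: the 0.0167 and 0.0125 values are conditional on one reading. It does not remove the gap, because a corrected test needs a stated family.

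The three-versus-four conflict is also weaker than it looks. The analysis section's own list has three post-discharge time points and agrees with Table 1, so three is the more natural divisor. The Study Calendar still disagrees.

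A reader might infer that the Bonferroni correction is nearly redundant because cumulative counts overlap. The simulation does not support this. Uncorrected testing at each visit would give 11% to 14% false positives, so a correction is needed if the visits are tested, and Bonferroni is then only mildly conservative. A reader might also infer an inflated error rate, but the plan errs the other way.

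On the intervals, simultaneous coverage is valid. The plan also promises counts and proportions for categorical variables, so anyone can recompute a 95% interval. The extra width is a reporting cost, not lost information.

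Finally, moving to 0.05 would remove the only multiplicity correction in the plan. With one readmission test there are no visits to correct over. The remaining issue is readmission's rank relative to the primary endpoint, and the fix must settle that.

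**Conclusion.** The point holds in a limited form. The readmission analysis applies Bonferroni to an undefined family with no deciding time point. If the family is the visits, the day-30 alpha is 0.0167 or 0.0125, and the choice can change a conclusion. Against a single test at 0.05, power falls from 80% to 65% or 61% at an assumed 33% versus 12.7%, and from about 35% to 21% or 17–18% at an assumed 20% versus 10%, both with 64 per arm. The first scenario is favourable: in the second, even the single test has low power. The alpha values and the 22% to 27% interval widening need no assumed rates, only the visit-family reading; the power and false-positive figures do depend on assumed rates.

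The documents do not support a claim that false positives are inflated, that the plan outright specifies a test at every visit, or that the primary analysis of the Comprehensive Complications Index is affected. This is a conservative and under-specified rule for what the Aim 2 text calls a secondary endpoint of a pilot. It is worth correcting because the better method costs almost nothing.

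**What to change.** In the Aim 2 text of section 13.2.1.2:

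1. Make the readmission comparison a single two-sided 0.05 test of the proportion of patients with any readmission from discharge to day 30, with a 95% interval for the risk difference.
2. Report the earlier visits, the 60- and 90-day windows and ER visits descriptively, with ordinary 95% intervals and no tests. The Bonferroni sentence can then be removed.

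Elsewhere:

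3. Align the readmission time points in the Study Calendar (section 10.0), Table 1 (section 11.1) and the time-point list in section 13.2.1.2.
4. State consistently that readmission is a secondary endpoint in the synopsis, section 13.1.1 and both parts of section 13.2.1.2.

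The cost is wording only, with no added patients or visits. The downside is that no formal claim can be made about readmission at the earlier visits, which Hypothesis 2.1 does not single out.
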